**Table 2: Timing Window Allowances for PK/PD Sampling, ECG, and Vital Sign Measurements**

Pharmacokinetic and Pharmacodynamic Sampling	
Timepoint	Tolerance Window
0 hour	-240 min to 0 hour
5 minutes post end-of-infusion	± 5 minutes
2, 4, & 6 hours post end-of-infusion	± 15 minutes
24 hours post end-of-infusion	± 60 minutes
48 hours post end-of-infusion	± 120 minutes
ECG	
Timepoint	Tolerance Window
5 minutes post end-of-infusion	± 10 minutes
Vital Signsa	
Timepoint	Tolerance Window
0 hour	-240 min to 0 hour
15, 30, and 45 minutes after start of infusion	± 5 minutes
60 minutes after start of infusion	± 10 minutes
30, 60 and 120 minutes post end-of-infusion	± 10 minutes

a: Vital signs to include blood pressure, pulse rate, respiratory rate, oral temperature, and pulse oximetry.

---

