Methodology	
Two cohorts of 8 eligible subjects each will receive 5 once-weekly 60-minute infusions of SYNT001 in planned doses of 10 mg/kg or 30 mg/kg. Based on review of safety, PD, and clinical outcomes of these 2 cohorts, a third cohort of up to 8 subjects may be treated at another dose, with a maximum dose of 45 mg/kg, but may also be lower than 10 mg/kg or between 10 and 30 mg/kg, inclusive.
 
  
 Cohort	No. of subjects	Dose	
   
 1	8	SYNT001 10 mg/kg	
 
 2	8	SYNT001 30 mg/kg	
  
 
Cohorts will be dosed sequentially beginning with Cohort 1. The first 2 subjects will be dosed at least 24 hours apart. A review of the 24-hour safety data for the first subject will be performed to ensure that there are no overt safety concerns before dosing the second subject. A review of the 7-day safety data for the first 2 subjects will be performed prior to dosing the remaining 6 subjects in the cohort. This evaluation will include a review of AE/SAE reports, vital sign assessments, physical examinations, ECGs, and clinical laboratory testing. The seriousness, severity, and relatedness of AEs/SAEs will also be considered in the safety evaluation. Safety data will be reviewed on a continuous basis throughout the study. All safety data and any available and relevant PD data through Day 42 (2 weeks after the last subject's last dose in Cohort 1) will be reviewed by a dose escalation committee before Cohort 2 is initiated. Escalation to Cohort 2 will proceed if there are no concerning safety signals and the review of available and relevant PD data supports advancing to a higher dose. The dose for Cohort 2 will be finalized after review of the safety and PD data, but will not exceed 30 mg/kg. Cohort 2 and Cohort 3, if added, will be dosed per the same schedule as Cohort 1.
 
On days where study drug is administered, vital sign and pulse oximetry measurements will be collected immediately prior to the infusion; 15, 30, and 45 minutes after the start of the infusion; at completion of the infusion; and 30 minutes, 1 hour and 2 hours following completion of the infusion.
 
On Days 0 and 28, PK blood samples will be collected prior to infusion start and then over the subsequent 48 hours. Subjects will remain at the clinic through the 6-hour PK sample collection and will return to the clinic for the 24- and 48-hour collections. Additional samples will be collected on Days 5 and 33.
	Cohort	No. of subjects	Dose	1	8	SYNT001 10 mg/kg	2	8	SYNT001 30 mg/kg

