- b: **Vital sign** measurements (sitting blood pressure, heart rate, respiratory rate, and oral temperature) to be obtained after 5 minutes of seated rest. Any abnormal measurements are to be repeated after 5 minutes of rest. On Days 0, 7, 14, 21, and 28 vital sign measurements will be collected immediately prior to the infusion; 15, 30, and 45 minutes after the start of the infusion; at completion of the infusion; and 30 minutes, 1 hour and 2 hours following completion of the infusion.
- c: **Pulse oximetry**: On Days 0, 7, 14, 21, and 28, pulse oximetry to be measured immediately prior to the infusion; 15, 30, and 45 minutes after the start of the infusion; at completion of the infusion; and 30 minutes, 1 hour and 2 hours following completion of the infusion.
- d: **Clinical safety labs**: hematology, clinical chemistry, and urinalysis (see [Section 6.7](#) for a complete list). Full clinical safety lab draws will be collected at Screening and on Days 0, 7, 14, 21, 28, 33, 42 and 56.
- e: **Pregnancy test**: To be performed at time of screening and prior to first dose of SYNT001 on Day 0 and on Day 56 (urine or serum test is acceptable, however, positive urine tests must be confirmed with serum testing.)
- f: Digital 12-lead **ECG** to be obtained after 5 minutes of rest in the supine position and in triplicate at least 1-2 minutes apart (see [Section 6.6](#) for additional information). On Days 0 and 28 to be obtained 5 minutes after the completion of infusion. Day 12 ECG will be collected only if the visit is conducted at the study site.
- g: **Serology**: Testing at Day 56 will not be done for any subject whose baseline titer is below the level of detection. If the Day 56 results are greater than 30% below the baseline value, or if the subject falls below the level of detection, the subject will be re-tested at 1 month after the Follow-Up visit (approximately 2 months after the subject's last dose); if still below the baseline value (or level of detection), the subject will be re-tested after another month (3 months after last dose). Any subject whose baseline value for tetanus or VZV was above the detectable level at baseline, and is not within 30% of the baseline value or is below the detectable level on Day 56 and upon 2 retests (2 and 3 months following last dose of SYNT001), will be referred to their primary care physician for further management. See [Section 6.7.3](#) for additional information.

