## 7 STUDY ASSESSMENTS

### 7.1 Screening Period: Day -14 to Day -1

Informed consent must be obtained before any study-specific samples are taken or study-specific tests or evaluations are conducted. The following assessments at the screening visit are to occur within 14 days before dosing. Study eligibility will be based on satisfying all the study inclusion and exclusion criteria.

At the screening visit, information will be collected and subjects will have clinical evaluations as follows:

- Informed consent ([Section 6.1](#))
- Medical history and demographic data ([Section 6.2](#))
- Review inclusion and exclusion criteria ([Section 5.2](#), [Section 5.3](#))
- Complete PE, including height and weight ([Section 6.3](#))
- Vital sign measurements (after 5 minutes of rest; sitting blood pressure, heart rate, respiratory rate, oral temperature); abnormal results to be repeated after 5 minutes of rest ([Section 6.5](#))
- 12-Lead ECG (to be obtained in triplicate after 5 minutes of rest in the supine position) ([Section 6.6](#))
- Clinical safety laboratory tests (hematology, serum chemistry panel, urinalysis) ([Section 6.7](#))
- Pregnancy test ([Section 6.7](#))
- Hepatitis and HIV screen ([Section 6.7](#))
- PD sample collection ([Section 6.7](#))
  - IgG, IgG subtypes (IgG1-4), IgA, IgM
  - Anti-Dsg (1 and 3) antibody titer
- Concomitant medication assessment ([Section 6.9](#))
- AE assessment ([Section 6.10](#))

### 7.2 Enrollment and First Treatment: Day 0

Study Day 0 is defined as the date the subject is administered their first dose of study drug. On Day 0, subjects will be asked to come to the clinic and the following procedures will be performed prior to the first dose of study drug:

- Complete physical exam ([Section 6.3](#))
- Vital sign measurements (sitting blood pressure, heart rate, respiratory rate, oral temperature); to be measured immediately prior to the infusion ([Section 6.5](#))
- Pulse oximetry (to be measured immediately prior to the infusion) ([Section 6.5](#))

- Clinical safety laboratory tests (hematology, serum chemistry panel, urinalysis) ([Section 6.7](#))
- Pregnancy test ([Section 6.7](#))
- Serum tetanus antibody and VZV antibody ([Section 6.7](#))
- PDAI Score ([Section 6.4](#))
- PK baseline sample collection (collected just prior to the start of the study drug infusion) ([Section 6.7](#))
- Immunogenicity sample collection (collected just prior to the start of study drug infusion) ([Section 6.7](#))

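### Table 2's four-hour tolerance for the pre-infusion vital signs and pulse oximetry is too wide for a reading set immediately before the infusion

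*Protocol*

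**What the plan says.** Table 2 of the protocol gives timing allowances in three blocks. In the Vital Signs block, the 0-hour row allows "240 min to 0 hour" (the 240 carries a minus sign), that is, any time in the four hours before the infusion starts. The next row, "15, 30, and 45 minutes after start of infusion", allows 5 minutes either side. The end-of-infusion and post-infusion rows allow 10 minutes either side. Footnote a brings oximetry under the same rows: "Vital signs to include blood pressure, pulse rate, respiratory rate, oral temperature, and pulse oximetry". The PK/PD block of the table has an identical 0-hour entry. The repeated copy of Table 2 in the document reads the same.

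Elsewhere the timing is much closer:

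- Synopsis, Methodology: "vital sign and pulse oximetry measurements will be collected immediately prior to the infusion". Section 4.3 says the same.
- Table 1, footnote b: "vital sign measurements will be collected immediately prior to the infusion".
- Table 1, footnote c: "On Days 0, 7, 14, 21, and 28, pulse oximetry to be measured immediately prior to the infusion".
- Section 7.2 (Day 0): "Pulse oximetry (to be measured immediately prior to the infusion". Sections 7.6, 7.8, 7.10 and 7.11 say the same for the later doses, and all five lists time the vital signs in the same way.

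Section 6.5 gives this timing for vital signs and refers the site to Table 2 for the allowances. No section narrows the four hours.

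**The concern.** The pre-infusion reading is the same-day reference against which a change during or after the infusion is judged. Section 9.6.1 describes infusion reactions as a possible risk of the drug, with typical onset between 30 minutes and 2 hours after the infusion starts. The signs listed there include changes in heart rate and blood pressure, and fever. These quantities can move within a few hours for reasons unrelated to the drug.

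A gap before dosing is plausible. The Section 7.2 list puts vital signs and oximetry near the top, ahead of laboratory draws, PDAI scoring, PK and PD samples, an optional biopsy and photography. Drug follows only when all of these are done. A site that worked down the list could have readings an hour or two old and still in window.

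Three uses of the data give the reading some weight. Vital signs are part of the primary safety measure (Section 4.2). Their change from baseline is to be summarized at each scheduled time point (Section 12.5). The dose escalation committee reviews them, including oximetry, before escalation (Section 11.5). A reading not taken close to the infusion cannot be recovered later by any analysis plan.

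**Working it through.** There is no sample size or error rate to reproduce. The check compares Table 2 with the schedule and counts what the row governs.

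**Permitted age of the reading (Table 2).**
- 0-hour vital signs and oximetry: up to 240 minutes before the start.
- Readings at 15, 30 and 45 minutes: departure of up to 5 minutes. 240 / 5 = 48.
- End of infusion, and 30, 60 and 120 minutes after it: departure of up to 10 minutes. 240 / 10 = 24.

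These ratios apply to the infusion-day rows of Table 2 only. Non-dosing visits have much wider windows in Table 1.

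**Period that the reading anchors.** Infusion 60 minutes + observation 120 minutes = 180 minutes. The allowance of 240 minutes exceeds this by 60 minutes.

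**Readings per infusion.** 1 before + 3 during (15, 30, 45 minutes) + 1 at the end + 3 after (30, 60, 120 minutes) = 8, so 7 follow the start.

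**Oximetry before any drug.** Table 1 schedules oximetry on the five dosing days only: 8 x 5 = 40 readings per subject. Section 7.1 lists the screening vital signs without it: "Vital sign measurements (after 5 minutes of rest; sitting blood pressure, heart rate, respiratory rate, oral temperature". The Day 0 pre-infusion value is therefore the only 1 of the 40 that precedes all drug. Over two cohorts of 8 that is 16 values; with a full third cohort, 24. Replacements are not counted.

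**All pre-infusion readings under the row.** 16 x 5 = 80, or 24 x 5 = 120 with a full third cohort. This is the reach of the row, not the number expected to be old.

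**Nearest earlier scheduled reading (Table 1).**

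| Dose (day) | Vital signs | Oximetry |
|---|---|---|
| 1 (Day 0) | screening, 1 to 14 days before | none |
| 2 (Day 7) | Day 5, 2 days before | 7 days before |
| 3 (Day 14) | Day 12, 2 days before | 7 days before |
| 4 (Day 21) | Day 19, 2 days before | 7 days before |
| 5 (Day 28) | Day 21, 7 days before | 7 days before |

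If the same-day reading is old, no other scheduled reading is a close substitute.

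**The case against.** The strongest reply is that a nominal time and a tolerance do different jobs. Every instruction that staff follow on a dosing day tells them to measure immediately before the infusion; Table 2 only decides when a departure is recorded as out of window. The protocol treats the PK sample, which is set just before the infusion, in the same way. The Day 0 workload makes a generous window an understandable operational choice. This stands: a reader might infer that Table 2 contradicts or cancels the instruction, but the texts can both be satisfied by measuring just before the start. What remains is that the table also accepts a reading that does not follow the instruction.

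A reader might also infer that dose decisions or toxicity grades are at risk. The documents do not support that. The stopping rules in Section 8.4 use graded, drug-related adverse events. Infusion reactions are graded on symptoms, interruption and treatment. CTCAE hypotension is graded mainly by intervention, and the hypoxia example is an absolute saturation. One Grade 2 hypertension criterion refers to previously normal values, but it does not say that this reading supplies them.

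The link to change from baseline is conditional. The protocol does not define the vital-sign baseline, and it does not say that the Section 12.5 summary includes oximetry: Table 1 and the visit lists keep oximetry separate from vital signs.

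Finally, Section 9.3 places dosing in the morning, so the four-hour extreme should be rare. That limits the problem but does not exclude a gap of an hour or two.

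**Conclusion.** The point holds as a cheap improvement. The textual mismatch is certain: the vital-sign row carries the same four-hour allowance as the blood samples, no section narrows it, and it is longer than the whole 180-minute period that the reading anchors. The consequence is a weaker same-day reference for acute changes and, on Day 0, for the only drug-free oximetry value.

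The effect on the safety results is not quantified and is probably small, because seven closely timed readings follow the start of each infusion and the visit lists already ask for the right timing. The counts of 80 or 120 readings might be taken as a number of compromised measurements; they are only an upper bound on what the row governs. Any effect on the change-from-baseline summaries rests on the assumption that the Day 0 pre-infusion value is the baseline.

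**What to change.** In the Vital Signs block of Table 2, and in its repeated copy, replace the 0-hour entry with a short window such as 30 minutes before the infusion to its start. Add that the reading is repeated if the infusion is delayed beyond that window. The 30 minutes is an assumed value for the sponsor to set; anything from 10 minutes (the tolerance already used in the block) to 60 minutes (the length of the infusion) would serve.

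Leave the PK/PD 0-hour row as it is. This is a judgement: a blood level before the first dose, or a week after the previous one, should change little in four hours, whereas vital signs can. The text elsewhere needs no change.

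The cost is one table cell and no new scheduled measurement. The downside is an occasional repeat reading or a few more recorded timing deviations.

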## LIST OF ABBREVIATIONS

ADA	Anti-drug antibodies
AE	Adverse event
AECA	Anti-epithelial cell antibody
ALT	Alanine aminotransferase
ANA	Antinuclear antibody
AST	Aspartate aminotransferase
ATC	Anatomical therapeutic chemical
AUC 0-24	Area under the plasma concentration-time curve from pre-dose (time 0) to 24 hours post-dose
AUC 0-∞	Area under the plasma concentration-time curve from pre-dose (time 0) to infinity
BLQ	Below the limit of quantification
BMI	Body mass index
BUN	Blood urea nitrogen
CAR-T	Chimeric antigen receptor and T-cell
CFR	Code of Federal Regulations
C3	Complement component 3
CBC	Complete blood count
CIC	Circulating immune complexes
CIDP	Chronic inflammatory demyelinating polyneuropathy
C max	Maximum plasma concentration determined directly from the concentration-time profile
CRO	Contract research organization
CV	Coefficient of variation
CVID	Common variable immune deficiency
DEC	Dose escalation committee
D5W	Dextrose 5% in Water
DIF	Direct immunofluorescence
DNA	Deoxyribonucleic acid
ECG	Electrocardiogram
eCRF	Electronic case report form
ESR	Erythrocyte sedimentation rate
FcGR2a	Fc Gamma R2a receptor
FcRn	Neonatal Fc receptor
FDA	Food and Drug Administration
GCP	Good Clinical Practice
GI	Gastrointestinal
HBV	Hepatitis B virus
HCV	Hepatitis C virus
HIPAA	Health Insurance Portability and Accountability Act
HIV	Human immunodeficiency virus
IB	Investigator's brochure
IC	Immune complex

---

ICF	Informed consent form
ICH	International Conference on Harmonization
IgA	Immunoglobulin A
IgG	Immunoglobulin G
IgG1-4	Immunoglobulin G1-G4
IgM	Immunoglobulin M
IL-12	Interleukin 12
IND	Investigational new drug
IRB	Institutional review board
ITT	Intent-to-treat
IUD	Intrauterine devices
IV	Intravenous
IVIG	Intravenous immunoglobulin
MedDRA	Medical Dictionary for Regulatory Activities
NHL	Non-Hodgkin lymphoma
PD	Pharmacodynamics
PE	Physical examination
PK	Pharmacokinetic
RBC	Red blood cells
RNAseq	RNA sequencing
QTcF	Corrected QT interval using Fridericia's formula
SAE	Serious adverse event
SAP	Statistical analysis plan
SAS	Statistical Analysis System
SD	Standard deviation
SNP	Single nucleotide polymorphism
SOC	System Organ Class
SOP	Standard operating procedures
SYNT001	A humanized, affinity matured IgG4-kappa monoclonal antibody
$t_{1/2}$	Half-life
TEAE	Treatment-emergent adverse event
$T_{max}$	Observed time to reach peak plasma concentration
TNF	Tumor necrosis factor
ULN	Upper limit of normal
UNS	Unscheduled
VZV	Varicella-zoster virus
WAIHA	Warm antibody autoimmune hemolytic anemia
WHO	World Health Organization
WHO-DD	World Health Organization Drug Dictionary

## 2 BACKGROUND AND RATIONALE

SYNT001, a humanized, affinity-matured IgG4-kappa monoclonal antibody (mAb), blocks IgG and IgG immune complex (IC) interactions with the neonatal Fc receptor (FcRn) and thereby the major functions of FcRn in protecting IgG and IgG ICs from degradation and their role in downstream signaling events. Specific and high affinity blockade of FcRn with SYNT001 has been shown to increase the catabolism of IgG and IgG IC in healthy volunteers. This predicts that SYNT001 will also accelerate degradation of endogenous circulating IgG autoantibodies and IgG-antigen IC specifically involved in the pathogenesis of autoimmunity. Blocking FcRn interactions with IgG-containing ICs further predicts that SYNT001 will have consequences for innate and adaptive cellular immunity. In the first instance, blocking multimeric IgG IC interactions with FcRn within antigen-presenting cells will result in inhibition of IC-stimulated inflammatory cytokine production and release by these cells. In addition, as FcRn determines the intracellular itinerary of IgG ICs within and among compartments important in cellular immunity, it is anticipated that SYNT001 will block antigen processing and presentation of antigens contained within IC that otherwise lead to CD8+ and CD4+ T cell activation. Thus, SYNT001 will specifically target immune functions associated with IgG that are involved in certain autoimmune conditions and dismantle their ability to cause disease.

SYNT001 targets key mechanisms contributing to pathology in a variety of IgG-mediated autoimmune disorders, including warm antibody autoimmune hemolytic anemia (WAIHA), pemphigus, and chronic inflammatory demyelinating polyneuropathy (CIDP).

While current treatments for certain autoimmune disorders, including high-dose steroids, immunosuppressants, intravenous immunoglobulin (IVIG), plasmapheresis, and anti-CD20 monoclonal antibodies (mAbs), such as rituximab, can be effective, they are associated with significant adverse effects, as well as delayed or non-durable responses.

Pemphigus is a rare group of blistering autoimmune diseases that affect the skin and mucous membranes. Autoantibodies have been shown to play an important pathogenic role in the mucosal and cutaneous manifestations in patients with pemphigus. Administration of SYNT001, which significantly decreases total IgG, including a corresponding decrease in the level of the pathogenic autoantibodies and the ICs to which they are associated, may lead to a decrease in the mucosal and cutaneous manifestations in patients with pemphigus. Moreover, the ability of SYNT001 to reduce circulating immune complexes (CICs) and the associated innate and adaptive immune responses may allow for further sustained disease modification.

## 2.1 Study Rationale

This study is being conducted to evaluate the safety, tolerability, pharmacokinetics (PK), pharmacodynamics (PD) and immunogenicity of intravenous (IV) SYNT001 as well as its effects on pemphigus disease activity markers.

## 2.2 Selection of Doses in this Study

The planned dose levels of SYNT001 for this Phase 1b safety and proof-of-concept study of 10 mg/kg and 30 mg/kg were selected from careful review of the safety, tolerability, and PD effect on total IgG levels after single and repeat dosing of SYNT001 in non-human primates (NHPs), as well as the safety, tolerability, and PD effect on total IgG levels after single ascending doses of SYNT001 in healthy volunteers. In addition, further consideration was given to the desired level of FcRn blockade to achieve suppression of IgG to a range that has been previously correlated with disease remission. Further, we considered the potential effects of inhibiting FcRn function as they relate to immune complex associated innate and adaptive immunity in choosing these dose levels based upon exploratory studies of a single ascending dose of SYNT001 in healthy volunteers. From the NHP studies, single doses of SYNT001 produced a dose-dependent decrease in total IgG and a further decrease was seen with repeated weekly doses up to a maximum 70% reduction at 100 mg/kg. This magnitude of total IgG reduction is approaching the expected maximal effect of 100% inhibition of FcRn function based on murine studies also performed by Syntimmune and others [[Roopenian 2003](#), [Nixon 2015](#)]. In the recently completed Phase 1a trial with SYNT001 in healthy volunteers a single dose caused a maximum average 50% drop in total IgG with IV dosing at 30 mg/kg. Based on the NHP studies further reductions are expected following multiple dosing. A comparable decrease in pathogenic autoantibodies is also anticipated.

In the NHP studies, relevant adverse effects, mild-to-moderate infusion reactions, were observed only after the third weekly IV administration, concurrent with the development of anti-SYNT001 antibodies. In the recently completed Phase 1a healthy male volunteer study, the doses of SYNT001 up to and including 30 mg/kg have been well tolerated. There were no dose limiting toxicities, serious adverse events, or any other safety concerns identified. No AEs were observed in the 1 and 3 mg/kg dose cohorts. A single Grade 2 AE was observed; a headache in the 10 mg/kg cohort, treated with acetaminophen. Other subjects had mild (Grade 1) AEs at 10 mg/kg. In Cohort 4 (30 mg/kg), 5 subjects received SYNT001. All five subjects experienced AEs; all were mild (Grade 1), transient and resolved spontaneously without intervention. Therefore, it is anticipated that the doses selected for this study should be well tolerated and have clinically relevant PD effects in patients with chronic pemphigus (vulgaris or foliaceus). For a summary of

findings from the single dose, clinical study in healthy subjects and further details on the nonclinical findings, please refer to the SYNT001 Investigator's Brochure.

